# 7.1.5.1 Fasting Prior to Scheduled Visits

Subjects should be counseled to fast (i.e., no food, double-blind investigational product, open-label AHA medication [metformin or sitagliptin (if applicable)], or drink except water and non-AHA non-investigational product as prescribed) for at least **10 hours** prior to all study visits. Subjects who do not fast before a scheduled visit will be required to return fasting for a study visit within three days. Subjects who have not fasted prior to Visit 1/Screening should obtain a fasting lipid profile and FPG at or prior to Visit 2 rather than Visit 1/Screening. Subjects who have not fasted prior to Visit 1/Screening are not eligible for a combined Visit 2/3.

#### 7.1.5.2 Scheduling Visits

At the end of each trial visit, the next trial visit should be scheduled. Every effort should be made to adhere to the visit schedule (see Section 6.0), and in general visits during the double-blind treatment period should be scheduled within +/-7 days (Visit 4/Randomization [Day 1] through Visit 8/Week 26) or within +/-14 days (Visit 9/Week 39 through Visit 14/Week 104). If unavoidable, a visit may be scheduled at a time outside of this recommended range, but the schedule for subsequent visits must be adjusted so that the total duration of the Phase A/Year 1 period is as close as possible to 52 weeks. Similarly, the total duration of the combined Phase A/Year 1 and Phase B/Year 2 periods (i.e., the period of time on blinded investigational product) should be as close as possible to 104 weeks. Visits should be scheduled relative to the date of Visit 4/Randomization (Day 1). If a visit is scheduled at a time other than the protocol designated time, careful consideration must be given to the amount of blinded investigational product the subject has available.

Trial sites should telephone the IVRS at each of the scheduled subject visits for purposes of enrollment tracking.

**Protocol/Amendment No.:** 002-01

Visit 2 or combined Visit 2/3 may be scheduled as soon as it is confirmed that the subject meets all Visit 1/Screening trial criteria, including laboratory criteria.

The double-blind treatment period begins at Visit 4/Randomization (Day 1). All subsequent double-blind treatment period visits should be scheduled relative to Visit 4/Randomization (Day 1).

# **Visit Reminders-Telephone Contacts**

Prior to each visit, subjects should be called to be reminded of:

- The date and time of appointment.
- The requirement to fast for at least 10 hours prior to the clinic visit.
- The requirement to not engage in physically strenuous exercise (i.e., lifting, weight training, calisthenics, and aerobics) within 48 hours prior to their clinic visit.
- The requirement not to take metformin, sitagliptin (if applicable) and blinded investigational product the morning of the clinic visit. Non-study medications that are not AHA medications should be taken as directed by the prescribing physician.
- The requirement to bring blinded investigational product, open-label AHAs, the blood glucose meter, the HAL and any collected SMBG information to the clinic.

# 7.1.5.3 Visit 1/Screening

Subjects will be consented and screened according to Visit 1/Screening Inclusion/Exclusion Criteria and will receive a screening number. The subject's medical history and prior/concomitant medications will be reviewed, and vital signs, body weight, and height will be measured. For subjects assessed as eligible to participate in the trial, fasting blood and urine samples will be obtained. Women of childbearing potential will have a urine pregnancy test performed (and serum pregnancy test if required by site's IRB/EC).

At the site, the investigator may choose to screen subjects with fingerstick A1C measurements (prior to drawing blood samples for the central laboratory screening measurements) to evaluate the likelihood of the subject subsequently meeting trial glycemic inclusion criteria. If, based upon the fingerstick A1C value, the investigator believes the subject is an unlikely candidate for the trial, the subject may be excluded prior to undergoing additional trial procedures. Investigators should be aware that the site-fingerstick A1C is a tool to evaluate a subject's glycemic status and that a central laboratory measured A1C is still required to assess A1C entry criterion at Visit 1/Screening.

**Note (1):** A subject excluded due to the TSH criterion may be re-screened after being on a stable thyroid replacement therapy for at least 6 weeks.

**Protocol/Amendment No.:** 002-01

**Note (2)**: Subjects with elevated TG levels may have lipid-lowering medication initiated or adjusted and continue in the trial if a repeat measurement at Visit 3/Week -2 no longer meets the exclusion criterion. Subjects who have lipid-lowering medication adjusted or initiated cannot have a combined Visit 2/3. Subjects on lipid-lowering medication must be on a stable regimen for at least 4 weeks prior to Visit 4/Day 1.

#### 7.1.5.4 Visit 2

At Visit 2, subjects who are (1) on metformin monotherapy  $\geq 1500$  mg/day for <8 weeks, (2) on metformin monotherapy <1500 mg/day or (3) on metformin (any dose) in combination with a single allowable AHA will begin the variable wash-off/titration/dose stabilization period. Subjects must be on a stable dose of metformin monotherapy  $\geq 1500$  mg/day for  $\geq 8$  weeks prior to Visit 3/Week -2. Subjects on metformin in combination with a SU must complete a  $\geq 10$  week dose stable period prior to Visit 3/Week -2.

All subjects will be evaluated according to Visit 2 Inclusion/Exclusion criteria. The subject's prior/concomitant medications and adverse events will be reviewed, vital signs, body weight, and height will be measured, and fasting urine samples obtained. All subjects will (1) have diet/exercise counseling, (2) receive glucose meters and training in performing SMBG, (3) receive instruction on hypoglycemia symptoms, hypoglycemia management, and completion of the HAL and (4) receive a Subject Identification Card.

Subjects will be instructed to monitor their fingerstick glucose concentrations with a frequency determined appropriate by the investigator (based upon his/her assessment of the subject's glycemic control) with a minimum of two fasting determinations per week. Subjects are to contact the site if they experience any episodes of hypo- or hyperglycemia.

# 7.1.5.5 Combined Visit 2/3 or Visit 3/Week -2: Single-blind Placebo Run-in

Subjects with T2DM who are on metformin monotherapy  $\geq 1500$  mg/day for  $\geq 8$  weeks prior to Visit 1/Screening with a Visit 1/Screening A1C of  $\geq 7.0\%$  and  $\leq 9.0\%$  [53 mmol/mol and 75 mmol/mol] and who meet all other enrollment criteria will be eligible to enter the single-blind placebo run-in at a combined Visit 2/3. All other eligible subjects will undergo a variable wash-off/titration/dose stabilization period prior to Visit 3/Week -2.

The subject's prior/concomitant medications, adverse events, SMBG measurements, and HAL will be reviewed. Vital signs, body weight, and height will be measured, and fasting blood and urine samples obtained. Additionally, a full physical exam, locally read 12-lead ECG and postural blood pressure and pulse will be performed. Women of childbearing potential will have a urine pregnancy test performed (and serum pregnancy test if required by site's IRB/EC).

**Protocol/Amendment No.:** 002-01

The first dose of single-blind placebo run-in (matching placebos for ertugliflozin and matching placebo for glimepiride 1 mg) must be taken as a witnessed dose in the clinic visit after completion of all combined Visit 2/3 or Visit 3/Week -2 procedures including the collection of all fasting blood samples. Subjects will take their single-blind placebo for approximately two weeks prior to randomization. Subjects should be reminded to withhold single-blind investigational product on the day of Visit 4/Randomization (Day 1).

#### 7.1.5.6 Treatment Period

#### 7.1.5.6.1 Visit 4/Randomization (Day 1)

At Visit 4/ Randomization (Day 1), subjects who meet all trial enrollment criteria will have all baseline laboratory tests and trial procedures performed and will be randomized in a 1:1:1 ratio to ertugliflozin 5 mg q.d., ertugliflozin 15 mg q.d., or glimepiride.

Each subject will be assigned only one randomization number; assignment of a randomization number will occur only at Visit 4/Randomization (Day 1).

Double-blind investigational product will be dispensed at Visit 4/Randomization (Day 1). The first dose of double-blind investigational product should be taken as a witnessed dose after completion of all trial procedures including the collection of all fasting blood samples.

# 7.1.5.6.2 Visit 5/Week 6 through Visit 14/Week 104: Double-Blind Treatment Period

Subjects will be dispensed double-blind investigational product at Visit 5/Week 6, Visit 6/Week 12, Visit 7/Week 18, Visit 8/Week 26, Visit 9/Week 39, Visit 10/Week 52, Visit 11/Week 65, Visit 12/Week 78 and Visit 13/Week 91.

The blinded investigational product dose must be taken orally in the morning at approximately the same time each day. If a subject misses a dose of blinded investigational product during the trial, they should be instructed to take it as soon as they remember unless it is time for the next dose. Subjects should be instructed not to "make up" for the missed dose by taking two doses at the same time. Compliance for the daily dosed medication will be determined by site performed tablet or capsules count.

# 7.1.5.7 14-Day Post Treatment Telephone Contact

A telephone contact will be performed 14 days after the last dose of blinded investigational product to collect SAEs and events eligible for adjudication.

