### Management of Randomized Subjects

At Visit 4/Randomization (Day 1), subjects will enter the 104-week, double-blind, active-comparator-controlled treatment period and be randomized in a 1:1:1 ratio to ertugliflozin 5 mg once-daily (q.d.), ertugliflozin 15 mg q.d., or glimepiride. Glimepiride/matching placebo will be initiated at 1 mg q.d. and titrated up to the maximum approved dose (6 or 8 mg q.d. based on the local country label) or maximum tolerated dose. Glimepiride/matching placebo may be down-titrated to avoid or manage hypoglycemia (see Section 5.2.1.2 for detailed instructions about titrating glimepiride). Subjects are to remain on their stable dose of metformin (≥1500 mg/day) while receiving blinded investigational product during the double-blind treatment period.

During Phase A/Year 1, subjects who are on the maximum labeled dose or maximum tolerated dose of glimepiride/matching placebo for at least two weeks and who meet progressively more stringent glycemic rescue criteria (see Table 6) will initiate open-label sitagliptin glycemic rescue medication in accordance with the local country label. Subjects who are rescued in Phase A/Year 1 will not be eligible to enter Phase B/Year 2. The study design does not include glycemic rescue therapy in Phase B/Year 2. During Phase B/Year 2, subjects who are on the maximum labeled dose or maximum tolerated dose of glimepiride/matching placebo for at least two weeks and who meet glycemic criteria specified in Section 5.8 will be discontinued from treatment with blinded investigational product.

Subjects who are discontinued from blinded investigational product for any reason other than withdrawal of consent will be followed by telephone contacts for the duration of the trial according to the Trial Flow Chart - Section 6.0. The purpose of these telephone contacts, as well as the 14-day post trial telephone contact, will be to collect SAEs and events eligible for adjudication (see Section 7.3.4).

This trial is designed to evaluate, in adult subjects with T2DM and inadequate glycemic control on diet and exercise and metformin, the effect of both the 5 and 15 mg doses of ertugliflozin on glycemic control, symptomatic hypoglycemia, body weight, and blood pressure following a 52-week dosing period. It is also designed to evaluate the long-term efficacy, safety and tolerability of ertugliflozin during the entire 104-week double-blind, active-comparator-controlled treatment period.

[figure not shown]

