#### 5.8.1 Follow-up for Subjects Who Discontinue Blinded Investigational Product

If the subject withdraws consent from participating in the trial, no further evaluations should be performed, and no additional data should be collected. The sponsor may retain and continue to use any data collected before the subject's withdrawal of consent.

Subjects who discontinue treatment with blinded investigational product for reasons other than withdrawn consent should attend the clinic for a discontinuation visit followed by a post-treatment telephone call 14 days after the last dose of blinded investigational product. Thereafter, subjects will be followed by telephone contacts according to the study schedule until the end of the trial (Week 104). The purpose of these telephone contacts, as well as the 14-day post-treatment telephone call, is to collect information about subjects' health status (e.g., evaluate if the subject experienced any SAEs or events eligible for adjudication [see Section 7.3.4]).

If a subject indicates his or her intention to stop active participation in the trial (i.e., chooses to no longer attend visits at the investigational site, take blinded investigational product, and have other study-related procedures conducted at the investigational site) or if the investigator has recommended withdrawal of the subject from active participation in the trial, the investigator must clarify with the subject if he/she is willing to continue in the study with contact at intervals to provide a brief and focused update on health status (e.g., evaluate if the subject experienced any SAEs or events eligible for adjudication [see Section 7.3.4]). It will be important for the subject to understand the importance of complete collection of information, and also the limited requirements for continuing to provide this information (i.e., a brief telephone contact, occurring at the time of the originally planned study visits). Thus, subjects may discontinue blinded investigational product and continue to receive telephone calls from the site or they may indicate that they do not wish to have further contact with the site.

Protocol/Amendment No.: 002-01

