		Phase	B/Year 2		Rescue	Post-1re	atment
Visit Number	11	12	13	14	Rescue c	Discontinuation	Follow-up
Scheduled Week	65	78	91	104		At time of Discontinuation d	14-Day Post Treatment Telephone Contact e
Clinic							
Review of SMBG Measurements and HAL	X	X	X	X	X	X	
Assess Subjects for Potential Rescue or Discontinuation from Blinded Investigational Product, Based on Central Laboratory FPG/A1C	X	X	X				
Adverse Event Monitoring	X	X	X	X	X	X	X
Laboratory Procedures/Assessmen	ts						
FPG	X	X	X	X	X	X	
A1C m	X	X	X	X	X	X	
Fasting C-peptide o					X	X	
Proinsulin o					X	X	
Lipid Panel p				X	X	X	
Chemistry Panel	X	X	X	X	X	X	
Hematology		X		X	X	X	
Urine Collection (Urinalysis and Urine Albumin/Creatinine Ratio) q		X		X	X	Х	
Urine Pregnancy Test (women of childbearing potential only) r	X	X	X	X	X	X	
Plasma and serum for Future Biomedical Research				X	X	X	

Trial Period :		Double-Blin	d Treatme	nt	Rescue	Post Treatment			
		Phase I	3/Year 2		Rescue	Post-Treatment			
Visit Number	11	12	13	14	Rescue c	Discontinuation	Follow-up		
Scheduled Week	65	78	91	104		At time of Discontinuation d	14-Day Post Treatment Telephone Contact e		

- a. Subjects on metformin ≥1500 mg/day for ≥8 weeks prior to Visit 1/Screening, with a Visit 1/Screening A1C ≥7.0% and ≤9.0% (≥53 mmol/mol and ≤75 mmol/mol) can directly enter a combined Visit 2/3. Subjects requiring adjustment of blood pressure or lipid-lowering medication and subjects who are not fasting at Visit 1 should NOT have a combined visit. All procedures performed at Visit 2 and Visit 3/Week -2 must be performed at the combined Visit 2/3.
- b. Site personnel will contact subjects to assess glycemic control and collect adverse events.
- c. Immediately prior to initiation of rescue medication (at a scheduled or unscheduled visit), subjects meeting rescue criteria must undergo the Rescue Visit procedures.
- d. Subjects who discontinue taking investigational product prematurely should complete procedures for the Discontinuation Visit. These subjects will also be contacted via telephone by the investigator/qualified designee according to the same schedule as if the subject were still taking investigational product to collect SAEs and events eligible for adjudication (see Section 5.8.1).

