- e. Subjects will be contacted 14 days after the final dose of blinded investigational product to collect SAEs and events eligible for adjudication.
- f. A subject ICF must be signed prior to any trial specific procedures being performed and may be signed prior to Visit 1/Screening.
- g. The Future Biomedical Research (FBR) informed consent must be obtained before FBR samples for DNA analysis, plasma, and serum are collected. The FBR sample for DNA analysis should be obtained pre-dose, at Visit 4/Randomization, as the last sample drawn, on randomized subjects only. The sample may be obtained at a later date during the trial after the FBR informed consent is obtained. The plasma and serum samples for FBR should be collected at Visit 4/Randomization (pre-dose), Visit 10/Week 52, Visit 14/Week 104 (or Discontinuation Visit), and Rescue Visit (if applicable). For the FBR serum and plasma, samples should be collected at all time points, even if the pre-dose or other time point was not collected.
- h. Subjects will be seen by a dietician or qualified healthcare professional for dietary and exercise counseling at Visit 2 or combined Visit 2/3; follow-up at other visits may be done by other appropriate site personnel evaluating the subject.
- i. The witnessed dose will be taken after completion of all procedures for the trial visit, including the collection of all fasting blood samples.
- j. Brief physical examination includes assessment of heart, lungs, abdomen, extremities and skin.
- k. Visit 3/Week -2 or combined Visit 2/3 ECG is read locally at the investigative site. ECG for all other time points should be submitted to be read centrally.
- 1. Site fingerstick A1C is not mandatory, but may be used, at the discretion of the investigator, for screening subjects. However, a fingerstick A1C cannot substitute for a central laboratory measured A1C to determine if a subject meets entry criteria.
- m. A1C should not be drawn if Discontinuation Visit or the Rescue Visit occurs within six weeks after Visit 4/Randomization (Day 1).
- n. Fasting C-peptide test at Visit 1/Screening is only for subjects assessed by the investigator as possibly having Type 1 diabetes.
- o. Fasting C-peptide and proinsulin should not be collected for subjects discontinuing in Phase B/Year 2.
- p. Includes total cholesterol, high-density lipoprotein (HDL-C) cholesterol, low-density lipoprotein (LDL-C) cholesterol, triglycerides and non-HDL at all time points.

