**Protocol/Amendment No.: 002-01** 

Adverse events may occur during the course of the use of the Sponsor's product in clinical trials or within the follow-up period specified by the protocol, or prescribed in clinical practice, from overdose (whether accidental or intentional), from abuse and from withdrawal.

Adverse events may also occur in screened subjects during any pre-allocation baseline period as a result of a protocol-specified intervention, including washout or discontinuation of usual therapy, diet, placebo treatment or a procedure.

All adverse events will be recorded from the time the consent form is signed through 14 days following cessation of treatment and at each examination on the Adverse Event case report forms/worksheets.

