# 8.2.3.2 Statistical Methods for Safety Analyses

Safety and tolerability will be assessed by clinical review of all relevant parameters including AEs, laboratory tests, vital signs and ECGs.

Safety analyses will be performed for three time periods: Week 0 to Week 52 (Phase A), Week 52 to Week 104 (Phase B), and Week 0 to Week 104 (Phase A+B). Phase A is considered the primary time period for safety evaluation. All safety endpoints will be analyzed for the Phase A and Phase A+B time periods. For the Phase B time period, only AEs and PDLC in laboratory parameters will be analyzed. The population for analyses of only Phase B will be all subjects who took at least one dose of study medication in Phase B.

Two sets of data will be considered: data pertaining to the Treatment Period and data pertaining to all post-randomization follow-up. For AEs, the Treatment Period dataset will include all data from randomization to 14 days after the final dose of study medication, with the exception of analyses of the Phase A Treatment Period, for which the 14 additional follow-up days will be included only for subjects who did not continue into Phase B. For laboratory endpoints, the Treatment Period dataset will include all data from randomization to 2 days after the final dose of study medication. The "all post-randomization follow-up" dataset, which applies only to SAEs, will include all data after randomization, with no upper limit on the follow-up window. Listings of AEs (regardless of seriousness) and of PDLCs occurring beyond the Treatment Period will be provided. Laboratory data collected after the Treatment Period will be summarized separately from Treatment Period data.

**Protocol/Amendment No.:** 002-01

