Two approaches will be used for handling data occurring after the initiation of glycemic rescue therapy. The first approach, which will be used for all safety endpoints in analyses of Phase A alone, will exclude all data following the initiation of rescue therapy at any timepoint, in order to avoid the confounding influence of the rescue therapy. The second approach, which will be used for all safety endpoints in analyses of Phase A alone and of Phases A+B combined, will include data following the initiation of rescue therapy. For analyses of Phase A alone, the "including rescue" approach will be considered primary for analyses of SAEs, discontinuations due to AEs, and ECGs, and the "excluding rescue" approach will be considered primary for all other endpoints. For analyses of hypoglycemia, the "excluding rescue" approach will be considered primary regardless of the time period being summarized. For analyses of Phase B alone, excluding/including rescue is not relevant, as there is no rescue therapy in Phase B.

Table 12 summarizes the analysis approaches for safety endpoints by study phase.

Study Phase(s)	Data Included	Endpoints	
A	Treatment Period data, ER	All safety endpoints	
	Treatment Period data, IR	All safety endpoints	
	All post-randomization data, IR	SAEs, Discontinuations due to AEs	
В	Treatment Period data	AEs, PDLCs	
A+B	Treatment Period data, IR	All safety endpoints	
	Treatment Period data, ER	Hypoglycemia	
	All post-randomization data, IR	SAEs, Discontinuations due to AEs	

Treatment Period includes up to 14 days post treatment for AEs, and up to 2 days post treatment for PDLCs.

ER = excluding data after initiation of glycemic rescue therapy

IR = including data after initiation of glycemic rescue therapy

The analysis of safety results will follow a tiered approach. The tiers differ with respect to the analyses that will be performed. Safety parameters or adverse events of special interest that are identified *a priori* constitute "Tier 1" safety endpoints that will be subject to inferential testing for statistical significance with p-values and 95% CIs provided for between-group comparisons. Between-group comparisons will be made between ertugliflozin and glimepiride. Other safety parameters will be considered Tier 2 or Tier 3. Tier 2 parameters will be assessed via point estimates with 95% CIs provided for between-group comparisons; only point estimates by treatment group are provided for Tier 3 safety parameters.

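### The documents conflict on whether the 14-day post-treatment call collects all adverse events or only SAEs and adjudicable events, so non-serious events in a window the SAP analyses may be unevenly ascertained

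*Combined protocol and SAP*

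**What the plan says.** Three places state a narrow purpose for the call.

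- Section 7.1.5.7: "A telephone contact will be performed 14 days after the last dose of blinded investigational product to collect SAEs and events eligible for adjudication".
- Flow chart (Section 6.0), footnote e, attached to the follow-up column: "Subjects will be contacted 14 days after the final dose of blinded investigational product to collect SAEs and events eligible for adjudication".
- Section 2.1, Management of Randomized Subjects: the purpose of the calls after discontinuation, "as well as the 14-day post trial telephone contact, will be to collect SAEs and events eligible for adjudication".

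Section 5.8.1 is looser. The purpose there "is to collect information about subjects' health status (e.g., evaluate if the subject experienced any SAEs or events eligible for adjudication", so the two categories are examples of health status and not a limit.

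Other places imply a wider scope.

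- The Adverse Event Monitoring row of the flow chart has an X in the 14-day follow-up column.
- Section 7.2: "All adverse events will be recorded from the time the consent form is signed through 14 days following cessation of treatment".
- Section 8.2.3.2: "For AEs, the Treatment Period dataset will include all data from randomization to 14 days after the final dose of study medication". The note to Table 12 repeats it: "Treatment Period includes up to 14 days post treatment for AEs, and up to 2 days post treatment for PDLCs".

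For the scheduled calls during treatment, footnote b uses general wording: "Site personnel will contact subjects to assess glycemic control and collect adverse events".

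**The concern.** The Tier 1 safety endpoints in Section 8.2.3.2 are urinary tract infection, genital mycotic infection, hypovolemia and symptomatic hypoglycemia. None is restricted to serious events. Symptomatic hypoglycemia also supplies the second and fifth of the six ordered confirmatory tests in Sections 8.1.3 and 8.2.5.

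All four are counted through 14 days after the last dose. If a site asks only about SAEs and adjudicable events at the contact that closes that window, a non-serious event in it enters the data only if the subject volunteers it or another contact picks it up. Section 8.2.2.2 bases safety analysis on observed data, without imputation unless noted otherwise. A subject whose only event was never asked about is therefore counted as event-free.

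What is at stake is consistent ascertainment across sites and subjects. In the Phase A analysis the 14 days count only for subjects who do not continue into Phase B, so any shortfall would sit in that group.

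**Working it through.** **Scope of collection against scope of analysis**

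| Place | Scope in the 14 days after the last dose |
|---|---|
| Section 2.1; Section 7.1.5.7; footnote e | SAEs and adjudicable events |
| Section 5.8.1 | Health status, with those two as examples |
| Flow chart, Adverse Event Monitoring row | Marked at the 14-day contact |
| Flow chart, review of glucose self-monitoring and the hypoglycemia log | Not marked at the 14-day contact |
| Section 7.2 | All adverse events recorded |
| Section 8.2.3.2 and Table 12 note | All adverse events analysed |

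Section 8.2.3.2 separates two datasets. The one covering all post-randomization follow-up applies only to SAEs; the Treatment Period dataset, which holds the 14-day tail, does not. The analysis plan therefore treats the tail as an all-event window on purpose. The flow chart contradicts itself: the row mark and the column footnote give different scopes for the same contact.

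**Size of the window**

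The plan states no figure for this, so there is none to reproduce. The inputs are the 14-day window (Section 8.2.3.2), 410 subjects per arm, and the cumulative attrition in Section 8.2.6: 0.073, 0.091, 0.112, 0.160, 0.210 and 0.312 at Weeks 6, 12, 18, 26, 39 and 52.

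1. Phase A+B, Week 104 completer: 14 / (104 × 7 + 14) = 14 / 742 = 1.9%.
2. Phase A, days on study per randomized subject, with attrition linear within each interval, is the sum of interval length × (1 − mean attrition over the interval):
   - 42 × 0.9635 = 40.467
   - 42 × 0.9180 = 38.556
   - 42 × 0.8985 = 37.737
   - 56 × 0.8640 = 48.384
   - 91 × 0.8150 = 74.165
   - 91 × 0.7390 = 67.249
   - Sum = 306.558 days; × 410 = 125,689 person-days per arm.
3. Phase A tail if all attrition counts: 410 × 0.312 = 127.9 subjects; × 14 = 1,791 person-days. Share = 1,791 / (125,689 + 1,791) = 1.4%.
4. If only 10% or 20% contribute a tail: 574 / 126,263 = 0.5%, and 1,148 / 126,837 = 0.9%.

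**Effect on the hypoglycemia comparison**

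Table 15 gives a detectable difference of 6.2 points at 90% power, with 5% on ertugliflozin and 410 per arm. The usual two-proportion formula for 5% against 11.2%, with pooled variance under the null, is:

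- Null SE = √(2 × 0.081 × 0.919 / 410) = 0.01906
- Alternative SE = √((0.05 × 0.95 + 0.112 × 0.888) / 410) = 0.01893
- z = (0.062 − 1.96 × 0.01906) / 0.01893 = 1.30, so power = 90.4%

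The plan's figure is therefore reproduced. Reducing both proportions by 1.4% gives 89.9%; reducing both by 1.9% gives 89.8%. These results assume a constant event rate, including after the drug is stopped, and equal loss in both arms.

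**The case against.** The strongest reply is that this is a matter of wording. The flow chart schedules adverse event monitoring at the contact, Section 7.2 independently requires every event to be recorded, and Section 5.8.1, which governs early leavers, permits a wider question. Other routes also exist. Early leavers have a Discontinuation Visit with adverse event monitoring and log review, and Section 7.1.5.9 contemplates that visit one week after the last dose for renal discontinuations. Section 7.1.1.8.2 tells subjects to report low fingerstick glucose values to the site.

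Most of this stands, and it rules out three stronger readings.

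- A reader might infer that non-serious events in the window are not collected at all. No passage says so, and the flow-chart mark and Section 7.2 point the other way.
- A reader might infer that the confirmatory hypoglycemia tests are materially compromised. Those tests are at Week 52. Subjects entering Phase B contribute no tail to them, and the primary analysis excludes post-rescue data.
- A reader might infer bias between arms from unequal early leaving. Repeated hypoglycemia is a discontinuation criterion in Section 5.8, so imbalance is possible, but Section 8.2.6 assumes one attrition schedule for all arms and nothing shows a difference.

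The reply does not remove the conflict. Footnote e sits on the same column as the X and narrows it, Sections 2.1 and 7.1.5.7 agree with the footnote, and the contrast with footnote b makes the narrow wording look deliberate. A site that follows Section 7.1.5.7 would ask the narrower question.

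**Conclusion.** The point holds as an inconsistency in the current text. Instructions for the 14-day call differ in scope, and the SAP analyses the wider one, so non-serious adverse events in the tail may be unevenly ascertained.

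The effect on the results is likely to be small. The tail is at most about 1.4% of Phase A person-time and about 1.9% of the Phase A+B period for a Week 104 completer. The illustrative loss of power for hypoglycemia is about half a percentage point. The 1.4% treats all assumed attrition as subjects who stop treatment and contribute a full tail. That attrition was set for the A1C calculation, where Section 8.2.3.1 also counts rescue as a source of missing data, and rescued subjects stay on blinded product. The primary hypoglycemia analysis also drops post-rescue data, so its share is smaller.

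SAEs and adjudicable events are named in every version of the call's purpose and are unaffected. This is a minor correction, worth making because it is cheap.

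**What to change.** Reword Section 2.1, Section 7.1.5.7 and footnote e so that the 14-day call collects all adverse events, and clarify the example in Section 5.8.1 to match. The text would then agree with the flow-chart mark, Section 7.2 and Section 8.2.3.2. Telephone contacts after that call stay limited to SAEs and adjudicable events, as footnote d already provides.

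The cost is a broader adverse event question on a call that already takes place. No endpoint, window or analysis changes. Tier 1 hypoglycemia needs no glucose value, so the question serves that endpoint without adding log review to the call.

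The other way to reconcile the text is to shorten the recording and analysis window for non-serious events. That would mean changing Sections 7.2 and 8.2.3.2 and giving up follow-up the protocol already requires, so it is the less attractive route.
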